## **8.0 CORRELATIVES/SPECIAL STUDIES**

The goal of the planned laboratory correlative studies is to measure the induced immune response to patient's pre-treatment tumor tissue antigens (see section 1.5 for detail). In addition,

the correlative studies will evaluate the immune response generated by the regiment. The submission of collected whole blood before, during and post treatment as indicated in Section 5 is mandatory and will be performed at baseline, during RT (1-2 hours after first SABR fraction), at 4 weeks and at 24 weeks. A CT-guided biopsy of a tumor lesion will be performed prior to study registration, unless previous biopsy of the primary lesion is performed within the last one year exists and a review of slides shows it to be adequate, in which case a pretreatment biopsy is optional. The one year post-treatment biopsy will be processed the same way as the pre-treatment biopsy.

## 8.1 Sample Collection Guidelines

Samples will be labeled with the subject's de-identified study number and collection date and delivered for analysis during regular business hours to: NC7: 208; Attn [name].

**8.1.1 Whole blood sample:** Patient's whole blood will be collected in EDTA (Lavender top) tubes for ~ 100 ml at baseline, at 4 weeks (+/- 1 week) and at six months starting from the first day of study registration for immunologic assays. In addition, 10 ml will be collected in anti-coagulant-free tubes (Red top) for the collection of sera. The only exception is the blood collection one hour post first SABR fraction which will be for 20ml in EDTA and 20 ml in anti-coagulant-free tubes. The blood will immediately be processed (within 2 hours) by centrifugation (1000g, 15min, 4 °C), collecting the supernatant and freezing at -80 °C in 5 aliquots for future experiments. The pellet will be re-suspended in PBS and PBMC will be isolated using standard protocol. Briefly, the cell suspension will be carefully placed on 10ml polystyrene tube containing 1ml ficoll and centrifuged (400g, 30min, RT). Collect the PBMC region from the ficoll and washed 3x with PBS. Count and freeze cells in 5 aliquots with 10%DMSO 90%FBS in -80°C.

**8.1.2 Renal mass biopsy sample:** An image-guided biopsy of tumor lesion consisting of 4-5 18G needle cores is recommended at the time of registration of the patients to the study. A second biopsy at one year after the SABR treatments is required.

**8.1.2.1 Initial required biopsy:** 3-4 core biopsies will be processed as routine diagnostic specimens by Pathology for the purpose of diagnosis and Immuno-histochemistry (IHC). After on site adequacy check using touch imprint slides, the cores will be fixed in 10% buffered formalin for up to 8 hours and processed routinely to obtain formalin fixed paraffin embedded blocks. Eight, 3-micron thick sections will be cut. The first and last sections will be stained with hematoxylin and eosin (H&E) stain to evaluate the presence, extent, and grade of renal carcinoma. The remaining sections will be used to perform immunohistochemical staining if needed. (see section 8.2.6 for IHC detail). **Two additional cores** will be placed in normal saline on wet ice and brought to NC9.208 ([name]) for generation of tumor lysates to be used as a source of antigen in the immunoassays. The biopsy cores will be chopped into minute pieces. Small volume of normal saline is added and the mixture is passed through a 19G needle, attached to a 5 ml syringe, several times, until the passage of the mixture occurred without difficulty. The process is repeated with 21G, 23G, and if possible 25G needle. The entire mixture is placed in liquid nitrogen until frozen, and then thawed in a water bath at 42°C. The freezing and thawing is repeated for a total of five times. The sample is passed through another 23G or 25G needle to disperse any clumps. The sample is then centrifuged at high speed, the

supernatant collected, protein concentration measured using NanoDrop2000 and frozen at -80 °C in 5 aliquots.

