#### 4.2.3 Treatment Timing and Duration

For a given lesion (target), a minimum of 40 hours and a maximum of 8 days should separate consecutive treatments. All treatment must be completed within 21 days.

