**5.0 STUDY PROCEDURES****5.1 Screening/Baseline Procedures**

Assessments performed exclusively to determine eligibility for this study will be done only after obtaining informed consent. Assessments performed for clinical indications (not exclusively to determine study eligibility) may be used for baseline values even if the studies were done before informed consent was obtained.

All screening procedures must be performed within two months prior to registration unless otherwise stated. The screening procedures include:

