**5.2.2 Day 1**

- First fraction of SABR
- Correlative Blood draw 1-2 hours after first SABR fraction only (see section 8).

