**5.2.3 4 weeks (+/-1 week) after treatment termination**

- Physical Exam: including: medical history and vital signs
- Hematology
- Serum chemistries
- Lab corollary blood draw
- Urine Analysis
- Performance status
- Toxicity evaluation

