**5.3 Follow-up Procedures**

Subject will be followed at every six months (+/- 2 weeks) thereafter for five years after their first follow up at 1 month (+/- 1 week).

With every visit, patients will have:

- Physical exam including: vital signs, weight, height and BMI
- MRI with or without contrast or CT with contrast
- Renal scintigraphy scan at 1 year
- Hematology
- Serum Chemistries
- Urine Analysis
- Lab corollary blood draw at 1 month and six month
- Performance status
- Toxicity evaluation
- Tumor measurements

**\*Note:** Subjects who show progressive disease or develop a new primary will be followed for survival only and will no longer strictly adhere to study calendar.

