**5.4 Time and Events Table**

	Pre-study Within 2 months prior to registration	Day 1 First SABR	At One month (+/- 1 week)	q6 Months (+/- 2 weeks)	At one year (+/- 2 weeks)
Assessment	X				
Informed Consent	X				
Diagnostic/ Pre- treatment Renal Bx	X				
Post-treatment Renal Bx					X
Physical Exam	X	X	X	X	
Performance Status	X		X	X	
Toxicity Evaluations			X	X	
Tumor Measurements	X			X	

Chemistry	X		X	X	
CBC	X		X	X	
Correlative Labs	X	X*	X*	X*	
Urine Analysis	X		X	X	
MRI or CT	X			X	
Renal Scan	X				X

\*Correlative labs will be drawn at baseline, on first day of SABR (see section 8), at one month and at 6 month after SABR.

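### Section 8.1.1 times the 4-week and six-month immune blood draws from registration, contradicting the post-SABR timing in Section 5

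*Protocol*

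**What the plan says.** Five places in the protocol set the timing of the post-treatment correlative draws.

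- **8.1.1 (whole blood sample):** "at 4 weeks (+/- 1 week) and at six months starting from the first day of study registration for immunologic assays". The time origin is registration.
- **5.2.3:** the correlative draw is one item of a visit held "4 weeks (+/-1 week) after treatment termination". The time origin is the end of SABR.
- **5.4, footnote to the Time and Events Table:** draws "at one month and at 6 month after SABR". The origin is SABR, without saying first or last fraction.
- **5.3:** "Subject will be followed at every six months (+/- 2 weeks) thereafter for five years after their first follow up at 1 month". The draws listed there are at 1 month and six months, and the six-monthly visits run on from the 1-month visit.
- **8.0, the parent of 8.1.1:** "The submission of collected whole blood before, during and post treatment as indicated in Section 5 is mandatory". It then names 4 weeks and 24 weeks with no origin of its own.

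On treatment timing, section 4.2.3 states: "All treatment must be completed within 21 days". It also requires 40 hours to 8 days between fractions. Section 3.0 does not allow treatment before registration. No section caps the interval from registration to the first fraction.

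**The concern.** Objective 2.3.1 asks what cytokine and immune changes SABR brings about, and sections 1.4.1 and 8.2 use the samples for before/after comparisons within each patient. Such a comparison needs the later sample to sit at a known and similar distance from treatment in every patient.

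On the registration clock, that distance depends on how long planning takes and on the fractionation chosen. One patient's 4-week sample could be weeks after the last fraction, another's between fractions, and another's before the first. With 16 patients, a few such samples could noticeably change a summary of the average effect. A post-treatment sample that was not taken at the right time cannot be recovered later.

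**Working it through.** No sample size, power or significance figure is involved. The check is calendar arithmetic.

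**Inputs**
- Day 0 = registration.
- g = days from registration to first fraction. The protocol does not give it; 0 to 42 is assumed here to show the range.
- D = days from first to last fraction. The minimum follows from 40-hour gaps: 2 × 40 h = 3.3 days for three fractions, 3 × 40 h = 5.0 for four, 4 × 40 h = 6.7 for five. The maximum follows from 8-day gaps and the 21-day limit: 2 × 8 = 16 days for three fractions. For four or five fractions the gaps alone would allow 24 or 32 days, so the 21-day limit applies.

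**Windows for the 4-week draw**
- Under 8.1.1: 28 ± 7 = days 21 to 35, whatever g and D are.
- Under 5.2.3: days g + D + 21 to g + D + 35.
- SABR course: days g to g + D.

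**When can one sample satisfy both sections?** The windows share a day only if g + D + 21 ≤ 35, that is g + D ≤ 14. Section 4.10 gives a treatment duration of 2 to 3 weeks (D = 14 to 21). On that duration, the only possibility is g = 0 with D = 14, and the shared day is day 35. With a one-week course, the low end of the range in the study summary, g must be 7 days or less.

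**Where does the 8.1.1 window fall?**

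| g (assumed) | D | Course (days) | 5.2.3 window (days) | The 15 days of the 8.1.1 window (days 21–35) |
|---|---|---|---|---|
| 0 | 7 | 0–7 | 28–42 | all after SABR; nominal day 28 is 21 days after the last fraction |
| 0 | 14 | 0–14 | 35–49 | all after SABR; nominal day 28 is 14 days after |
| 14 | 7 | 14–21 | 42–56 | 1 in the course, 14 after |
| 14 | 14 | 14–28 | 49–63 | 8 in the course, 7 after |
| 14 | 21 | 14–35 | 56–70 | all 15 in the course |
| 28 | 14 | 28–42 | 63–77 | 7 before SABR, 8 in the course |
| 42 | 14 | 42–56 | 77–91 | all 15 before SABR |

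For any D, the whole 8.1.1 window precedes the first fraction once g exceeds 35 days. The nominal day 28 falls inside the course when g is 7 to 28 (D = 21), 14 to 28 (D = 14) or 21 to 28 (D = 7).

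**Six-month draw.** Four descriptions stand side by side: six months from registration (8.1.1), 6 months after SABR (5.4), six months on from the 1-month visit (5.3), and 24 weeks with no origin (8.0). Read literally, 5.3 gives about seven months after treatment, while 24 weeks is 168 days. The registration clock shortens the interval from the last fraction by g + D, which is 35 days when g = 14 and D = 21.

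**After correction.** If the 4-week draw is counted from the last fraction everywhere, it falls 21 to 35 days after that fraction for every g and D.

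**The case against.** **Section 5 may already govern.** Section 8.0 defers to it, 5.2.3 ties the draw to a clinic visit after treatment, and 5.4 agrees that it follows SABR. Against these stands one clause in a paragraph on tube handling. It could also be read loosely as saying when collection begins. This makes it likely that the intended clock is post-SABR. It does not remove the conflict: the plain reading of 8.1.1 is a time origin, and nothing says which section prevails.

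**The worst cases rest on an assumed gap.** This stands. With a short gap and a short course, the 8.1.1 sample is entirely post-treatment, only earlier than 5.2.3 intends. A 21-day course cannot arise with three fractions.

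**A reader might infer that mid-course samples will be analysed as post-treatment, because the laboratory works from 8.1.1.** The protocol supports neither step. It does not say which section the laboratory follows. Section 8.1 has every sample labelled with its collection date, so a mistimed sample can be identified, and section 9.3 promises only exploratory analysis with no rule that pools by nominal visit.

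**A reader might also infer that the early draw and its baseline are faulty.** Section 5.2.2 has "Correlative Blood draw 1-2 hours after first SABR fraction only", where 8.1.1 says one hour; one hour lies within that range, so this is looser wording. The baseline comparator is a screening draw, and section 5.1 says "All screening procedures must be performed within two months prior to registration unless otherwise stated". Sections 5.1.10 and 5.4 specify this consistently, and no passage promises a same-day pre-dose sample. Moving that draw to Day 1 would be a design preference, and by the volumes in 8.1.1 it would put 100 + 10 + 20 + 20 = 150 ml on one treatment day.

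**Conclusion.** The contradiction is real: 8.1.1 counts from registration, while 5.2.3, 5.4 and (by reference) 8.0 count from treatment. For the 4-week draw the two windows are disjoint unless gap plus course is 14 days or less. Within the protocol's own limits, a sample taken as 8.1.1 directs could be post-treatment, mid-course or pre-treatment. The mid-course and pre-treatment cases depend on a registration-to-SABR gap that the protocol neither states nor limits, so their frequency is unknown.

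An origin at the end of treatment is explicit only for the 4-week draw. The six-month draw lacks a single anchor even outside 8.1.1, so correcting 8.1.1 alone would not settle it.

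The effect is confined to exploratory objective 2.3.1. The primary endpoint, the sample size, and the secondary and safety endpoints are untouched. It should be corrected because the correction is simple and a mistimed sample cannot be replaced.

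**What to change.** 1. In 8.1.1, delete the clause that counts from registration and time the 4-week (± 1 week) draw from the last SABR fraction, as 5.2.3 does.
2. Choose one post-SABR anchor for the six-month draw, state whether it runs from the first or last fraction, and use it in 5.3, the 5.4 footnote, 8.0 (now 24 weeks) and 8.1.1.

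Both are wording changes. They add no draws and no blood volume, and leave the baseline and Day 1 draws as they are. For samples already collected, the recorded collection dates allow the interval from the last fraction to be computed, so any drawn before or during SABR can be identified.

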#### 8.1.2.2 **One-year Biopsy:** Processed same as initial biopsy.

### 8.2 **Assay Methodology**

- 8.2.1 ELISpot:** IFN- $\gamma$  ELISpot assays will be performed according to manufacturer's protocol using a commercial ELISpot kit (MabTECH). Briefly, 96 well plates are coated overnight with 0.015 mg/ml of an anti-human IFN-g monoclonal antibody. PBMC from patients will be incubated in triplicates wells and stimulated in the presence of either protein lysate from patient biopsy (50 $\mu$ g/ml) or 5 ng/ml PMA and 0.5 ng/ml ionomycin as positive control and albumin as negative control. For ELISPOT assays, plates are incubated for 48 hours, washed, probed with biotinylated anti-IFN $\gamma$ , further washed, and then incubated with streptavidin alkaline phosphatase. Spot development is achieved with 5-bromo-4-chloro-3-indolyl phosphate/nitroblue tetrazolium (BCIP/NBT; Invitrogen) and spots are enumerated by an automatic ELISpot reader.
- 8.2.2 ELISA:** In this procedure, patient tumor tissue lysate is first adsorbed to an EIA 96 well microplate (Fischer). Patient plasma is then added to each well as a source of primary antibody and serially diluted. After extensive washes, detection enzyme (HRP)-linked anti-human mAb is then added to each well and allowed to bind. Appropriate substrate is then added to each well and color development occurs within 5-60 min. UV Microplate Reader will be used to read the plates
- 8.2.3  $^3$ H-thymidine Proliferation Assay:** PBMC from patients will be incubated in a similar manner as above for five days at 37 °C then overnight with 0.5 mCi tritiated  $^3$ H-thymidine, harvested onto a glass-fiber filter using a 96-well FilterMate cell harvester. The radioactivity of the  $^3$ H-thymidine is detected by a direct betaplate counter. The degree of antigen-specific clonal T cell expansion will be expressed as a stimulation index (SI) of the ratio of  $^3$ H-thymidine incorporation by cells incubated with patient tumor lysate compared with media controls. An alternate method utilizing FACS analysis with carboxy fluorescein diacetate succinimidyl ester (CFSE) is also available [95].
- 8.2.4 Chromium Release Cytotoxicity Assays:** For cell-mediated cytotoxicity analysis, A 50  $\mu$ l sample of  $^{51}$ Cr-labeled target cells (Caki-2 and ACHIN human renal cancer cells) is mixed with 100 $\mu$ l of effector cells (patient PBMC) at various target to effector ratio (E:T ratios). After centrifugation at 100 X G, the cells are incubated for 2 hr at 37°C. The radioactivity of culture supernatant is measured using a gamma counter and percentage of cytotoxicity is calculated. For antibody-dependent cytotoxicity analysis this procedure will be performed with patient's plasma instead of PBMC and the percentage of cytotoxicity is calculated in similar manner. An alternate and non-radioactive labeling method utilizes GAPDH enzyme release from lysed cells called Bioluminescence Non Radioactive Cytotoxicity Assay (aCella-TOX, T Cell Technology, INC) [96, 97].
- 8.2.5 Flow cytometric analysis (FACS):** For FACS analysis of cell-surface molecules, the cell samples are stained with fluorescent dye – conjugated monoclonal antibodies against the selected markers on ice followed by fixation with 4% paraformaldehyde. Data are acquired on a LSRII (BD Biosciences) and analyzed using FACSDiva software (BD Biosciences). The PBMC of each patient before and after treatment will be analyzed to identify the relative sub-population of CTLs,

regulatory T-Cells, effector memory T cells, MDSCs, neutrophils and NK cells utilizing appropriate cell surface markers (see section 1.5).

**8.2.6 Immunohistochemical staining (IHC):** Standard immunohistochemistry staining procedure will be performed using the Benchmark XT automated stainer (Ventana) for both antibodies. Briefly, formalin-fixed, paraffin-embedded tissue sections will be cut at 3-4 micron and air-dried overnight. The sections will be deparaffinized, rehydrated, and subjected to heat-induced epitope retrieval. Sections will then be incubated with appropriate primary antibody. For signal detection, ultraView universal detection system (Ventana) will be used. The slides will be developed using 3-3'-diaminobenzidine chromogen and counterstained with hematoxylin. Appropriate positive and negative controls will be utilized for each run of immunostains. The evaluation of the immunostaining will be carried out by a genitourinary pathologist without knowledge of any clinicopathologic data. Only nuclear reactivity will be considered positive. An H score will be assigned as the product of average intensity of staining (0 for negative, 1 for weakly positive, 2 for moderately positive, and 3 for strongly positive) and extent of immunoexpression (0-100% percentage of cells staining). In addition, Dual-antibody ISH will be performed to identify and analyze TILs, CTL (CD3+, CD8+), Tregs (CD4+FoxP3), DC (CD11c), NK/T (CD3+, CD1d), neutrophils (CD11b, Ly6G) and MDSC (CD14+, CD11b) in the tumor tissue before and after treatment, when available (see section 1.5).

**8.2.7 Serum Cytokine Analysis:** Multiplex cytokine analysis in patient's plasma will be performed in precoated 96 well plates (Human TH1/TH2 10 plex ultrasensitive assay, Meso Scale Discovery – MSD, Maryland, USA) according to manufacturer's instructions. 25 µL of diluent 2 is dispersed into each well. The plate is sealed and incubated by vigorous horizontal shaking for 30 minutes at RT. 25 µL of the patient plasma is added per well and all samples measured in triplicates. Plates are sealed and incubated by vigorous horizontal shaking for two hours at RT. Plates are washed three times with 0.05% Tween 20 in PBS. 25 µL of 1× detection antibody solution is placed per well and sealed plates are incubated by vigorous horizontal shaking for two hours at RT. Plates are washed three times with 0.05% Tween 20 in PBS. 150 µL of 2× Read Buffer T is added to each well. Plates are analysed using the MSD SECTOR Imager 2400 and Discovery Workbench 3.0 software (both from Meso Scale Discovery, USA). The mean value of two wells is taken as the recorded reading, provided that the coefficient of variation (CV) was less than 10%. Concentrations recorded lower than the standard curve are kept as absolute values. For purposes of logarithmic analysis, readings of 0 are adjusted to 0.01 pg/ml. The following cytokines will be measured before and after treatment for each patients: Th1/Th2/Th17 cytokines, IFN-γ, IL-1β, IL-2, IL-4, IL-5, IL-8, IL-10, IL-12p70, IL-13, IL-17 TNF-α; pro-inflammatory cytokines: GM-CSF, IFN-γ, IL-1β, IL-2, IL-6, IL-8, IL-10, IL-12p70, TNF-α; Chemokines: Eotaxin, MIP-1β, TARC, IP-10, IL-8, MCP-1, MCP-4 and others including IL-6, TGF-β and HMGB1 (see section 1.5).

**8.2.8 Western-blot/Immuno-blot:** Caki-2 and ACHIN human renal cancer cells lysate will be used to perform immune-blott using plasma collected from patients before and after treatment. The Caki-2 and ACHIN cell 10^6 cells/mL will be lysed in immunoprecipitation assay buffer on ice for 30 min. Standard western blot methodology will be utilized. Briefly, 400 µg of protein will be separated using pre-made gradient 4% to 12% Bis-Tris gels (Invitrogen, Burlington, ON, Canada) and transferred to nitrocellulose. Patient sera/plasma will be diluted 1/500 in Blotto (5% dry milk powder; 0.1% Tween 20; 50 mmol/L Tris; 150 mmol/L NaCl) and incubated with nitrocellulose membranes for 1 h at room temperature using a multichannel immunoblotting device (Mini Protean II Multiscreen, Bio-Rad,

Mississauga, ON, Canada). The membrane will then incubated for 1 h at room temperature with horseradish peroxidase–conjugated goat anti-human IgG (H+L; Jackson ImmunoResearch, West Grove, PA) diluted 1/10,000 in Blotto and visualized by enhanced chemiluminescence.

**8.2.9 Gene expression analyses:** The current Illumina whole genome DASL platform allows for the interrogation of over 29,000 genes based upon the RefSeq (Build 36.2, release 38) database. This assay requires 50-200 ng of total RNA from archival FFPE samples or 10-100 ng total RNA from fresh frozen tissue. RNA will be isolated using the one column protocol from the Roche High Pure miRNA Paraffin Kit, which isolates total RNA, including miRNA. A 3mm x 10um section is sufficient to generate 200 ng total RNA from archival specimens. A cDNA pool is created using oligodT and random primers. The cDNA pool is interrogated using a paired 5' and 3' gene-specific 50-mer probes (annealing and selection) that also contain universal primer sequence. Probe extensions are ligated and then PCR amplified using the universal primer pairs. The PCR product is captured using standard Illumina bead technology and hybridized to the Illumina HT12 V4 chip and scanned. Expression values are highly reproducible ( $r^2 > 0.97$ ) and are similar to results by qPCR ( $r^2 > 0.85$ ). mRNA expression of specific genes by qRT-PCR will serve to validate DASL results as needed. Caki-2

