The correlative studies will explore the mechanisms of possible immune enhancement by SABR. Activation of each arm of the immune response will be evaluated separately utilizing different assays. The humoral response will be evaluated using ELISA to measure the titer of tumor-specific antibodies generated by SABR against tumor tissue collected from the respective patients and established human renal cancer cell line Caki-2 (clear cell) and ACHIN (adenocarcinoma). An overall increase in tumor antigen-specific antibody will be measured using immunoblotting with patient sera as a source of primary antibody.

Enhancements of increased cytotoxicity to renal cancer cells can be measured by cytotoxicity assays. Antibody-dependent cell-mediated cytotoxicity (ADCC) measures the cell-killing ability of certain lymphocytes that require the target cell to be marked by an antibody and thus measures the humeral response [69]. On the other hand, lymphocyte-mediated cytotoxicity assay will measure the formation of tumor-specific CTLs among the lymphocytes collected from patients with the controls being lymphocytes collected from the same patients before SABR. Since it is not practical or feasible to obtain sufficient quantities of tumor cells from each patients to assess a quantitative cytotoxicity by these assays, established allogenic human renal cancer cell line Caki-2 and ACHIN will be used for this purpose. It is a generally accepted principle of tumor immunology that there will be many common tumor antigens between different patient tumors of same site origin, and therefore tumor cell lines as well [69]. In fact, the tumor antigens (PSA, CEA, CA 19-9 etc.) that are in clinical practice are reported to be present in a significant portions

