### **2.4.3 Exploratory Endpoint:**

- 2.4.3.1 Immune Response: Immune response will be measured using ELISpot assay, T-cell proliferation assay, Immunoblot and ELISA.

2.4.3.2 Spatial-temporal radiographic tumor features predictive value: Predictive value of each feature for SABR treatment response will be assessed using the area under the receiver operating characteristic curve.

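### Section 8.2.4 runs the antibody-dependent cytotoxicity assay without effector cells, so it cannot measure the ADCC that section 1.4.1 plans

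*Protocol*

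**What the plan says.** Section 1.4.1 of the protocol sets out two cytotoxicity assays. One is ADCC, which it says "measures the cell-killing ability of certain lymphocytes that require the target cell to be marked by an antibody" and treats as a reading of the humoral response. The other is lymphocyte-mediated cytotoxicity, meant to show tumour-specific cytotoxic T cells. Because too few tumour cells can be had from each patient, "established allogenic human renal cancer cell line Caki-2 and ACHIN will be used for this purpose".

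Section 8.2.4 gives the bench method and also has two arms. In the cell-mediated arm, chromium-labelled Caki-2 and ACHIN cells are mixed with "effector cells (patient PBMC) at various target to effector ratio (E:T ratios"), incubated, and read by the radioactivity of the supernatant. In the antibody-dependent arm the same procedure is run with the patient's "plasma instead of PBMC and the percentage of cytotoxicity is calculated in similar manner".

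Section 8.1.1 describes how the two blood components are obtained. The patient's "whole blood will be collected in EDTA (Lavender top) tubes" and centrifuged. One step is "collecting the supernatant and freezing at -80 °C in 5 aliquots for future experiments". The next is: "The pellet will be re-suspended in PBS and PBMC will be isolated using standard protocol". A smaller volume is drawn without anticoagulant for serum.

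Section 2.4.3.1 lists the exploratory immune endpoint: "Immune response will be measured using ELISpot assay, T-cell proliferation assay, Immunoblot and ELISA". Neither cytotoxicity assay is in that list.

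**The concern.** By the protocol's own definition, ADCC needs three things in the well: a target cell, antibody bound to it, and a lymphocyte to do the killing. The method in 8.2.4 takes out the lymphocytes in order to put in the antibody. This is not a detail left for a laboratory manual. A procedure is stated, and it does not serve the purpose stated for it in section 1.4.1.

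At stake is the interpretation of one correlative. Among the humoral tests described, ELISA and immunoblot show whether antibody binds; ADCC is the one meant to show whether bound antibody leads to killing. If the assay is run as written, a low result says nothing about ADCC, and a raised result would carry the wrong name. If laboratory staff notice and add effector cells on their own initiative, neither the source nor the ratio is fixed. Both could then differ between samples taken before and after SABR, which is the comparison of interest. Section 10.6 also requires the study to be run as the approved protocol describes, so an unrecorded repair is not a sound way out.

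**Working it through.** No sample size, power or error rate is involved, so the check compares what each section puts in the well.

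1. **Required by the definition (section 1.4.1).** Antibody-marked targets and lymphocytes that kill them.

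2. **Cell-mediated arm (section 8.2.4).** 50 µl of labelled targets plus 100 µl of effector cells, which are the patient's PBMC. Targets: present. Effectors: present.

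3. **Antibody-dependent arm (section 8.2.4).** The same procedure with plasma in place of PBMC. Targets: present. Antibody, if the patient has made any: present in the plasma. Effectors: none. The wording is substitution, not addition.

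4. **Could plasma carry the effectors?** No. In section 8.1.1 the supernatant is removed and frozen, and PBMC are isolated separately from the pellet.

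5. **Could the targets act as effectors?** No. Caki-2 and ACHIN are tumour cell lines chosen to be killed.

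6. **Is another effector source named?** No donor PBMC, NK-cell preparation or effector line is specified for this assay. The non-radioactive alternative at the end of 8.2.4 changes how lysis is read (enzyme release instead of chromium), not what is in the well.

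7. **Do the arms match the planned assays?** Section 1.4.1 names two assays and 8.2.4 describes two arms. The PBMC arm is the lymphocyte-mediated assay, so the plasma arm is the only candidate for ADCC.

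With E effector cells and T target cells per well, the plasma arm has E = 0, so E:T = 0:T whatever T is. Release attributable to ADCC as defined in 1.4.1 is therefore nil by construction. Total release need not be nil: spontaneous release and any lysis caused by plasma itself remain, and the documents give no figure for either.

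**The case against.** The strongest reply is that 8.2.4 speaks of antibody-dependent cytotoxicity, omits the words cell-mediated, and contrasts this arm with the cell-mediated one. A plasma-only assay fits those words. This reading is possible, and the fix must allow for it. It does not remove the conflict, because section 1.4.1 names ADCC as the assay and no other method is given for it. Under this reading the fault lies in the name and in 1.4.1, not in the wells.

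A second reply is that the consequences are small. That stands. The assay is exploratory, it is outside the list in 2.4.3.1, section 9.3 plans only exploratory analysis of immune response, and the ELISA and immunoblot of the humoral response do not depend on it.

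Several stronger readings are tempting, and the documents do not support them:

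- **That percent cytotoxicity cannot be computed without an effector-to-target ratio.** It can. Section 8.2.4 derives the percentage from supernatant radioactivity; the ratio is a condition of the well, not shown as a term in the percentage.
- **That EDTA rules out complement lysis, so specific lysis must be about 0% in every sample.** The protocol does not discuss complement and gives neither the assay medium nor the final EDTA concentration. It also collects serum, and refers to serum and plasma loosely for the immunoblot in 8.2.8. No lysis figure can be derived.
- **That the trial will report a false negative on functional antibody.** No section commits to a conclusion based on this assay.

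**Conclusion.** The point holds as an internal contradiction between sections 1.4.1 and 8.2.4. Followed as written, the antibody-dependent arm cannot measure ADCC, and any release it shows is spontaneous or plasma-mediated.

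The size is limited to the meaning of one exploratory correlative under objective 2.3.1. The primary and secondary endpoints, the 16-patient sample size, the error rates and patient safety are unaffected. It should be corrected because the text is wrong on its face and the repair is small, not because the main result is at risk.

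The conclusion rests on reading the substitution of plasma for PBMC literally, and on the absence of any other effector source in the protocol. A separate laboratory procedure that adds effectors would mend the practice, but the protocol text would still need to agree with it.

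**What to change.** In section 8.2.4, specify the antibody-dependent assay as labelled Caki-2 or ACHIN targets, plus patient plasma or serum (one of the two, used throughout, from before and after SABR), plus one fixed effector source at a constant effector-to-target ratio. The source could be a single donor PBMC lot for all samples, or the patient's own baseline PBMC for all of that patient's time points if the aliquots suffice. Add two controls: targets with effectors but no plasma, and targets with plasma but no effectors. Compare the values before and after SABR over these controls.

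If a plasma-only assay was intended, give it a name that does not imply cell-mediated killing and correct section 1.4.1, so that its result is not reported as ADCC.

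The cost is a short wording change, some control wells, and either a donor lot or some frozen PBMC. No additional patient procedure is needed. The one constraint to check is supply: section 8.1.1 freezes PBMC in 5 aliquots, and ELISpot, proliferation, cell-mediated cytotoxicity at several ratios and flow cytometry also use PBMC. The protocol gives no cell yield or allocation, so it does not show that baseline aliquots can be spared. A donor lot avoids that question.
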